7.2. Primary and Key Secondary Efficacy Endpoint Estimands

7.2.1. Primary Efficacy Endpoint

Variable: Response, defined as improvement from baseline at Day 90 above Carney-Schlauch 95% upper confidence limits in Word Recognition in Quiet (Maryland CNC) in treated ears.

Population: The analysis population will be the FAS.

Intercurrent events: Subjects who discontinue the study early will be considered missing at random, and their last non-missing observation will be carried forward (i.e., if their Day 60 improvement is above Carney-Schlauch 95% upper confidence limit, then their Day 90 results will be assumed to also be above the limit).

Population-level summary: Comparison of responder proportions between treatment groups at the Day 90 visit.

Additional details on the computation, analysis, and sensitivity analyses for the primary endpoint can be found in Section 7.3.1.

7.2.2. Key Secondary Efficacy Endpoint

Variable: Change from baseline in percentage of recognized words overall at Day 90 in Words-in-Noise in treated ears.

Population: The analysis population will be the FAS.

Intercurrent events: Subjects who discontinue the study early will be assumed missing at random and missing responses will be taken into account using the model-based approach of MMRM.

Population-level summary: Comparison of mean difference between treatment groups at the Day 90 visit in change from baseline in percentage of recognized words.

Additional details on the computation, analysis, and sensitivity analyses for the key secondary efficacy endpoint can be found in Section 7.4.2.

7.2.3. Other Key Secondary Efficacy Endpoints

Variables: PGI-C hearing loss scale response and PGI-C daily impacts scale response at Day 90.

Population: The analysis population will be the FAS.

Intercurrent events: Subjects who do not have these assessments completed at Day 90 will be assumed missing at random, and no responses will be imputed.

Population-level summary: Comparison of mean difference between treatment groups at the Day 90 visit.

Additional details on the computation, analysis, and sensitivity analyses for these secondary efficacy endpoints can be found in Section 7.5.2 and 7.5.4.

7.3. Word Recognition in Quiet: Maryland CNC and W-22

Word recognition will be measured separately with recorded Maryland CNC and W-22 word lists. Both tests will consist of 50 words presented to the subject and the percentage of words correctly identified will be recorded separately for each test. If all 50 words are not assessed in an ear, the WR test score will not be calculated for that ear.

Word recognition will be performed at the Screening/Start of Lead-In, Lead-In, End of Lead-In/Treatment, Day 30, Day 60, Day 90, Day 180, and Day 270 visits. For Screening/Start of Lead-In, testing will be performed at 30 dB sensation level (SL) regarding the pure tone average of 0.5, 1, and 2 kHz at Screening/Start of Lead-In. For Lead-In and all subsequent visits (End of Lead-In/Treatment, Day 30, Day 60, Day 90, Day 180, and Day 270) testing will be performed at 30 dB SL regarding the pure tone average of 0.5, 1, and 2 kHz at Lead-In. If 30 dB SL is at an uncomfortable listening level for the participant, testing will be performed at the participant's most comfortable listening level. Word lists will be rotated at each visit.

For speech perception, WR in Quiet (Maryland CNC) will be used for the primary analyses. All analyses will be repeated using WR in Quiet (W-22) for supplementary analyses.

Word Recognition in Quiet results will be presented in a data listing for subjects in the FAS.

- 7.3.1. Improvement from baseline above Carney-Schlauch upper confidence limits
 - Computation of the Endpoint

Improvement is defined as an increase in post-baseline WR score above the Carney-Schlauch (2007) 95% upper limit based on baseline (average of Lead-In and End of Lead-In/Treatment scores) assessment. Subjects with improvement will be computed as 1, and as 0, otherwise for each visit and by ear (left, right). Missing values will be imputed using LOCF. Left and right ears will be mapped to treated and untreated for analysis. The incidence of WR improvement will be computed as the proportion of subjects who have a WR in Quiet improvement.

The Carney-Schlauch 95% confidence intervals (2007) reported in Section 14.2 will be used directly and not computed.

• Analysis of the Endpoint

The incidence of WR improvement will be summarized descriptively for treated and untreated ears separately by visit and treatment group for subjects in the FAS.

The primary efficacy analysis will be conducted for the incidence of WR improvement at Day 90 in treated ears for subjects in the FAS using a 1 degree of freedom Chi-Square test for a single 2x2 table without stratification. Although the randomization was stratified by Visit 2 WR Maryland CNC score (>= 28% vs < 28%) and laterality of hearing loss (bilateral vs unilateral), the randomization was done to maintain balance among the treatment groups across the randomization factors to help interpretation of the results rather than any prognostic status. As such, it is believed the unstratified primary analysis will be more straightforward in interpretation, especially if some of the sample sizes in individual strata are small.

• Sensitivity Analyses of the Endpoint

The Chi-Square test will be repeated using treated ears for subjects in the PPAS. Additionally, the Chi-Square test will be performed with improvement being defined as an increase in post-baseline WR score above the 90%, 85%, and 80% upper limit based on baseline assessment using Carney-Schlauch method for treated ears. The 90%, 85%, and 80% upper limits will be determined based on simulation using the same approach used to compute the 95% limits described by Carney-Schlauch (2007).

A two-sided 95% CI for the odds ratio for the incidence of improvement between the treatment groups for treated ears will also be computed using the Cochran-Mantel-Haenszel (CMH) chi-square test, adjusted for the randomization stratification factors.

A GEE model will be utilized to estimate an odds ratio and its associated 95% CI between the treatment groups at each visit for treated ears. With the binomial distribution assumption and logit link, the model will include fixed effects of treatment group, visit, interaction between visit and treatment group, baseline WR score, interaction between baseline WR score and visit, and randomization stratification factors. The model will utilize an unstructured working correlation matrix. If the model fails to converge, the randomization stratification factors will be excluded from the model. The odds ratios along with 95% CIs and p-values between treatment groups will be reported by visit.

An analysis will be conducted for the incidence of WR improvement at Day 90 using the DerSimonian and Laird method. In treated ears only for subjects in the FAS, a 2-sided 95% CI for the difference between treatment groups in incidence of WR improvement at Day 90 will be computed by the method of DerSimonian and Laird, using a fixed-effects model (setting the variance in treatment effects, Δ^2 , equal to zero), adjusting for the randomization stratification factors. The weighted difference in the incidence of improvement, 95% CI, and p-value can be determined by the following formula:

$$\hat{\theta} = \frac{\sum_{i=1}^{4} w_i \hat{\theta}_i}{\sum_{i=1}^{4} w_i} \sim N(\theta, 1/\sum_{i=1}^{4} w_i)$$

Where $\hat{\theta}_i$ is the difference in the incidence of improvement at Day 90 of the ith stratum and $w_i = 1/\text{var}(\hat{\theta}_i)$. The DerSimonian and Laird methodology is consistent with inverse variance weighting methodology. If the analysis cannot be performed using both randomization factors (4 strata) due to no variation within 1 or more randomization strata, the analysis will be performed using the single randomization factor (2 strata) that produces more similarly sized strata. Scatter plots displaying the percentage of recognized words (Section 7.3.2) at baseline versus post-baseline, along with the Carney-Schlauch confidence intervals, will be generated for each visit separately for treated and untreated ears.

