### **Exploratory Endpoint(s)**

- Audiometry, speech perception measure improvements, and safety assessments beyond Day 90

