### **10.4 End of Study Definition**

A participant is considered to have completed the study if he or she has completed all follow-up visits, including Visit 6 (Day 90).

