7.1.3. Timing of Analyses

[figure not shown]
termination or unscheduled visit data to scheduled visits.

Primary efficacy analysis will be conducted after all subjects have either completed the follow-up visits (Day 30, 60, and 90 visits) or early discontinued from study. Primary analysis will be performed in an unblinded fashion for analysis purposes while subjects not completing the observation visits will continue to be followed as being blinded to treatment assignment. Final CSR analyses will be performed after the study is completed, and the database is locked.

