7.1.6. Imputation Rules for Partial/Missing Data

Based on previous studies of FX-322, there is expected to be a very minimal amount of missing data in this study. Missing data for endpoints for word recognition in quiet using Carney-Schlauch confidence intervals will be assumed missing at random and will be imputed using the last observation carried forward (LOCF). Missing data for the key secondary endpoint for WIN improvement will be assumed missing at random and will be taken into account using the model-based MMRM approach. Missing data for PGI-C analyses will not be imputed. Missing data for other endpoints will remain missing in the planned statistical summaries and analyses.

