The primary analysis for the key secondary endpoint, WIN improvement based on mean change from baseline in percentage of recognized words overall at Day 90, will be based on the following MMRM model. In treated ears only for subjects in the FAS, post-baseline treatment group comparisons through day 90 will be performed using a MMRM model for change from baseline in percentage of recognized words overall with fixed covariates for treatment group, visit, interaction between visit and treatment group, baseline WIN score overall, the interaction between baseline WIN score overall and visit, and randomization stratification factors. If the model fails to converge, the randomization stratification factors will be removed from the model. An unstructured covariance will be used to model the within-subject errors. Linear contrasts will be constructed to estimate the treatment effect for the mean change from baseline in percentage of recognized words overall by visit (e.g., estimated Least squares (LS) Mean differences by visit).

Line graphs (with standard error bars) will be created for the adjusted (least squares) mean change from baseline in percentage of recognized words overall estimates for treated ears by post-baseline visit and treatment group for subjects in the FAS. Post-baseline visit will be plotted on the x-axis and the adjusted (least squares) mean change from baseline in percentage of recognized words overall estimates for treated ears will be plotted on the yaxis. Each treatment group will be presented as a separate line in the plot.

• Sensitivity Analyses of the Endpoint

The MMRM will be repeated using treated ears for subjects in the PPAS.

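### LOCF for the Carney-Schlauch word-recognition responder has no end visit, so untested subjects keep their earlier status at Days 180 and 270

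*SAP*

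**What the plan says.** SAP 7.3.1 sets the responder flag to 1 when the score exceeds the Carney-Schlauch 95% upper limit, and to 0 "otherwise for each visit and by ear (left, right). Missing values will be imputed using LOCF". SAP 7.1.6 says that missing data for these endpoints "will be assumed missing at random and will be imputed using the last observation carried forward (LOCF". Neither section names a last visit. SAP 7.3 lists Days 180 and 270 among the test visits and repeats all analyses for W-22. The incidence in 7.3.1 is tabulated by visit and arm in the FAS, and the 7.3.1 GEE is to "estimate an odds ratio and its associated 95% CI between the treatment groups at each visit for treated ears".

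The Day 90 estimand (SAP 7.2.1) says: "Subjects who discontinue the study early will be considered missing at random, and their last non-missing observation will be carried forward". Its only illustration is Day 60 carried to Day 90.

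Other parts of the plan stop at Day 90. In the WIN analysis (SAP 7.4.2), "post-baseline treatment group comparisons through day 90 will be performed using a MMRM model". The MMRMs in 7.3.5 and 7.4.5 and the audiometry GEEs in 7.6.5 and 7.7.5 carry the same limit.

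The protocol's exploratory endpoints are "Audiometry, speech perception measure improvements, and safety assessments beyond Day 90". Protocol 15.5 leaves subjects with missing data out of descriptive calculations. SAP section 11, on changes from the protocol, is marked not applicable.

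**The concern.** A carried-forward flag at Day 180 or 270 is not an observation. In a by-visit table it looks the same as one, and in a GEE it adds apparent information. If responders lose their gain after Day 90, those not tested still count as responders, and the arm with more Day 90 responders gains more from this.

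Some late gaps are plausible. Protocol 10.4 treats a subject as having completed the study once he or she has "completed all follow-up visits, including Visit 6 (Day 90"), so the observation visits lie beyond formal completion. Whether an effect lasts is a question the sponsor cares about: the protocol's Introduction says that gains in earlier responders were maintained at retest 1-2 years later. A table that partly copies Day 90 into Day 270 would be weak evidence on that question.

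**Working it through.** **Step 1. Which analyses are exposed?** The problem needs both LOCF and no Day 90 limit.

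| SAP analysis | LOCF? | Limited to Day 90? |
|---|---|---|
| 7.3.1 Carney-Schlauch incidence by visit | yes | no |
| 7.3.1 GEE | yes | no |
| 7.3.1 scatter plots (use the 7.3.2 score) | no | no |
| 7.3.2 percentage of words | no | no |
| 7.3.4 gain of at least 10%, table and GEE | no | no |
| 7.3.6 Thornton-Raffin incidence | no | no |
| 7.4.3 and 7.4.6 WIN responders, tables and GEEs | no | no |
| 7.3.5, 7.4.2, 7.4.5 MMRMs | no | yes |
| 7.6.5, 7.7.5 audiometry GEEs | no | yes |

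Only the first two rows meet both conditions, each for Maryland CNC and again for W-22.

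**Step 2. What the plan gives.** SAP 2.5 has 112 evaluable subjects and 10% dropout: 112/0.90 = 124.4, against a stated 124, or 62 per arm. It gives no responder rates (the detail is in the unmasked addendum) and no missingness after Day 90. The rest is therefore a scenario.

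**Step 3. Assumed inputs.**
- Day 90 responder rate on FX-322: 34%. This is the figure the protocol's Introduction gives for the open-label study FX-322-111, which used a different definition (an absolute gain of at least 10%).
- Day 90 rate on placebo: 10%.
- True late rate: 5% in both arms, whatever the Day 90 status.
- Share missing at the late visit, m: 0 to 20%, equal in both arms and unrelated to response.

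**Step 4. Rate shown under LOCF** = (1 - m) × late rate + m × Day 90 rate.
- m = 10%: FX-322 0.90 × 0.05 + 0.10 × 0.34 = 7.9%; placebo 0.90 × 0.05 + 0.10 × 0.10 = 5.5%.
- m = 20%: FX-322 0.80 × 0.05 + 0.20 × 0.34 = 10.8%; placebo 0.80 × 0.05 + 0.20 × 0.10 = 6.0%.

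The true difference is zero and the observed-case rates stay at 5% in each arm.

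**Step 5. Rejection rate.** Take two independent binomials with 62 per arm at the Step 4 rates, and sum the probability of all outcomes where the uncorrected two-sided 5% chi-square test rejects. This test stands in for the late-visit GEE contrast.

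| Missing | FX-322 shown | Placebo shown | Difference | Test rejects |
|---|---|---|---|---|
| 0% | 5.0% | 5.0% | 0.0 points | about 5% |
| 5% | 6.5% | 5.3% | 1.2 points | about 6% |
| 10% | 7.9% | 5.5% | 2.4 points | about 8% |
| 20% | 10.8% | 6.0% | 4.8 points | about 16% |

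**Step 6. Apparent persistence.** If a fraction q of Day 90 responders truly remain responders, LOCF shows m + (1 - m)q. With q = 50% this is 0.10 + 0.90 × 0.50 = 55% at 10% missing, and 0.20 + 0.80 × 0.50 = 60% at 20% missing.

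**Step 7. When there is no bias.** If m = 0, or if the late rate equals the Day 90 rate in each arm, the Step 4 formula returns the true rate. If late rates rise above Day 90, LOCF understates them.

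**The case against.** The other side has several good points.

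- **Little may be missing.** SAP 7.1.6 expects very few gaps, and Protocol 11.1 asks for every effort to complete the observation visits. This stands: the size of the distortion is unknown.
- **LOCF carries non-response too.** It freezes status in both directions and overstates durability only under net fading. This stands.
- **Unimputed late data are planned.** These are 7.3.2, 7.3.4, 7.3.6 and the 7.3.1 scatter plots, and SAP 5.1 reports by arm how many complete Days 180 and 270. This limits the harm. Still, no observed-case Carney-Schlauch incidence is planned, and the Thornton-Raffin table would treat the same absent subjects differently.
- **The protocol leaves room.** Protocol 15.7 lets the SAP specify exceptions on missing data, so LOCF is not barred. But the 15.5 statement on descriptive analyses carries no exception of its own, and section 11 does not mention the difference.

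A reader might also infer two things that the documents do not support. The first is that all the GEEs share the problem. Those in 7.6.5 and 7.7.5 stop at Day 90, and those in 7.3.4, 7.4.3 and 7.4.6 use endpoints that are not imputed. The second is that the primary-analysis cut would fill future visits with copies of Day 90. SAP 7.1.3 says only that the primary analysis runs "while subjects not completing the observation visits will continue to be followed", with final analyses after study completion. It does not say that late tables are produced at the first cut, or that visits not yet due count as missing.

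**Conclusion.** The rule has a gap: followed literally, it places carried-forward status at Days 180 and 270 in one by-visit table and one GEE, each for two word lists, and it differs from Protocol 15.5 without a record in SAP section 11. It would be too strong to say that the imputation creates durability. That needs both material late missingness and net fading, and the documents establish neither.

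Under the assumed fading (34% versus 10% at Day 90, 5% in both arms later, 62 per arm, missingness unrelated to response), a nominal 5% late-visit test rejects about 8% of the time at 10% missing and about 16% at 20%. With no late gaps there is no distortion.

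The primary and key secondary tests are all at Day 90 and are untouched, as is the fixed-sequence error control. The severity is minor and confined to exploratory late results, but the correction is cheap.

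**What to change.** - In SAP 7.1.6 and 7.3.1, limit LOCF to visits through Day 90.
- For Days 180 and 270, report the Carney-Schlauch incidence as observed cases, with the number tested per arm.
- In the 7.3.1 GEE, use no LOCF-filled values after Day 90. Either stop the model at Day 90, as the MMRMs do, or include the later visits as observed.
- In SAP section 11, record the use of LOCF as a departure from Protocol 15.5. The entry is needed for visits through Day 90 as well, because the descriptive table uses filled values there.

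The GEEs in 7.3.4, 7.4.3 and 7.4.6 need no change for this reason. Cutting them at Day 90 would remove modelled late comparisons that are not imputed.

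The cost is SAP wording and smaller denominators at Days 180 and 270. Observed-case rates are themselves unbiased only if absence is unrelated to response, which is why the number tested should be shown beside them.

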7.1.7. Summary of Endpoints and Analysis Methods

To assess treatment effect if no rescue medication is available, for efficacy analyses, assessments performed on or after date of rescue medication or therapy taken during the follow up period will not be included in the analyses. Specifically, rescue medication includes intratympanic steroid administered in the treated ear after study drug administration through Day 90 visit. A summary of endpoints and analysis methods is presented in Table 7-2.

Table 7-2 Endpoints and Analysis Methods

Endpoint	Analysis Method(s)	Section
Word Recognition in Quiet (Maryland CNC) and Word Recognition (W-22)*		7.3

Endpoint	Analysis Method(s)	Section
Improvement from baseline above Carney-Schlauch	 Descriptive summary for treated and untreated ears Brimary Analysis: Chi Square test for treated ears 	7.3.1
upper confidence limits (Primary Endpoint)	 Primary Analysis: Chi-Square test for treated ears Sensitivity Analysis: Chi-Square test for treated ears in PPAS 	
	 Sensitivity Analysis: Chi-Square test for treated ears based on improvement from baseline above 80%, 85%, and 90% Carney-Schlauch upper confidence limits 	
	Sensitivity Analysis: CMH test for treated ears	
	Sensitivity Analysis: GEE in treated ears	
	• Sensitivity Analysis: DerSimonian and Laird (1986) estimation for treated ears using both randomization factors (4 strata) as defined in Section 2.3. If the analysis cannot be computed using both randomization factors, the analysis will be performed using the single randomization factor (2 strata) that produces more similarly sized strata.	
	Scatterplots for treated and untreated ears	
	Descriptive summary for treated ears by site	
Percentage of recognized words	Descriptive summary for treated and untreated ears	7.3.2
Change from baseline in percentage of recognized words	 Descriptive summary for treated and untreated ears Line graphs (with standard error bars) for observed mean change from baseline for treated ears 	7.3.3
Improvement ≥10% (5 words) from baseline in percentage of recognized words	Descriptive summary for treated earsGEE in treated ears	7.3.4
 Line graphs (with standard error bars) for adjusted least squared means in change from baseline for treated ears MMRM in treated ears 		7.3.5
Improvement from baseline above Thornton-Raffin upper confidence limits	 Descriptive summary for treated and untreated ears Scatterplots for treated and untreated ears 	7.3.6
Words-In-Noise*		7.4

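### The stratified sensitivity CI for the Day 90 responder difference weights four small strata by their own estimated variances, so at design-size effects its nominal 95% coverage is about 86-93%

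*SAP*

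**What the plan says.** The primary estimand in SAP 7.2.1 is summarised as "Comparison of responder proportions between treatment groups at the Day 90 visit". SAP 7.3.1 tests it "using a 1 degree of freedom Chi-Square test for a single 2x2 table without stratification". One reason given for leaving out the strata is ease of interpretation, "especially if some of the sample sizes in individual strata are small".

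The sensitivity analyses in 7.3.1 then include a two-sided 95% CI for the difference in incidence at Day 90. It "will be computed by the method of DerSimonian and Laird, using a fixed-effects model" over the four strata formed by Visit 2 Maryland CNC score (28% or more against less) and laterality. Each weight is the inverse of the variance of that stratum's difference. How that variance is estimated is not stated.

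The fallback to two strata is worded in two ways:
- SAP 7.3.1: "If the analysis cannot be performed using both randomization factors (4 strata) due to no variation within 1 or more randomization strata".
- SAP Table 7-2: "If the analysis cannot be computed using both randomization factors, the analysis will be performed using the single randomization factor (2 strata".

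No other overall Day 90 difference has a CI with a stated method. The CMH analysis gives "A two-sided 95% CI for the odds ratio for the incidence of improvement between the treatment groups", the GEE also gives odds ratios, and the by-arm table is descriptive: "The incidence of WR improvement will be summarized descriptively for treated and untreated ears separately by visit and treatment group". Section 7.8 promises 95% CIs for non-stratified subgroup differences and names no method. The protocol synopsis promises a 95% CI of the difference between arms in general terms.

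**The concern.** Inverse-variance weights behave well when each stratum variance is well estimated. Here the strata average 62/4 = 15.5 subjects per arm, and responders may be few. A stratum that happens to have few responders has a small estimated variance, so it is taken to be precise and dominates the pooled estimate. Those strata also tend to show small differences, so the estimate is pulled down, and the pooled standard error comes out too small. The SAP gives small strata as a reason to keep the primary test unstratified, then uses a stratified method that is sensitive to them.

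What is at stake is the stated size and precision of the effect in the one stratified difference that readers will set beside the primary result. The two fallback wordings add a second problem: two programmers could run different analyses on the same data.

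**Working it through.** **The plan's own figure.** Enrolment reproduces: 112/0.9 = 124.4, and 112 × 1.1 = 123.2, rounded up to 124. The 80% power cannot be reproduced, because SAP 2.5 leaves the detail to the restricted addendum.

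**Inputs.** From the documents: 62 per arm, four strata, two-sided 95%, weights 1/variance. Assumed:
- Per-arm stratum sizes of 16/16/15/15, 20/11/20/11, 24/14/14/10 and 30/10/16/6.
- Placebo rates of 1-15%, with FX-322 rates that give the chi-square 84-91% power.
- Unpooled variances.

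**Formulas.** For stratum i with n_i per arm:
- d_i = p1_i − p0_i and v_i = p1_i(1−p1_i)/n_i + p0_i(1−p0_i)/n_i
- w_i = 1/v_i, estimate = Σ w_i d_i / Σ w_i, SE = 1/√Σ w_i

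**Fallback.** Reading A: two strata are used when some v_i = 0. Reading B: two strata are used when any arm within a stratum has all or no responders.

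**Mechanism, on one made-up data set.** Strata 16/16/15/15; FX-322 responders 1, 4, 4, 6; placebo 0, 1, 1, 2.
- d_i = 0.0625, 0.1875, 0.2000, 0.2667
- v_i = 0.00366, 0.01538, 0.01719, 0.02370
- Weight shares: 62%, 15%, 13%, 10%
- Inverse-variance result under reading A: 11.9 points (2.5 to 21.3). Under reading B: 16.3 (4.8 to 27.9).
- Crude difference: 15/62 − 4/62 = 11/62 = 17.7 points.
- Mantel-Haenszel weights n_i/2 = 8, 8, 7.5, 7.5: (0.5 + 1.5 + 1.5 + 2.0)/31 = 17.7 points (Sato 5.7 to 29.7).

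The first stratum holds about a quarter of the subjects and takes 62% of the weight. The example shows the mechanism and is not typical: at equal placebo rates of 5-15%, a gap of 5.8 points or more from the crude difference occurs in 0.5-5.3% of trials.

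**Coverage.** 40,000 simulated trials per scenario, equal rates across strata; ranges are over the four splits:

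| Placebo / FX-322 | Reading A | Reading B | Mantel-Haenszel/Sato |
|---|---|---|---|
| 1 / 14% | 86-89% | 87-91% | 92-93% |
| 2.5 / 17.5% | 88-90% | 91-92% | 94-95% |
| 5 / 22.5% and 5 / 25% | 89-91% | 92-93% | 94-95% |
| 10 / 31% | 91-92% | 93% | 94-95% |
| 15 / 38% | 92% | 93% | 94-95% |

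Unstratified Newcombe intervals cover 95-97% in the same trials. With placebo rates that differ by stratum and a constant 20-point difference, reading A covers 90-92%, reading B 93-94% and Mantel-Haenszel/Sato 94-95%.

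**Direction of the misses.** At placebo rates of 1-5%, about 5-13% of intervals lie wholly below the true difference and 1-2% wholly above; the estimate is biased down by about 0.4-2 points. Near a 15% placebo rate the misses are roughly balanced, and under reading A the mean standard error is about 10% below the true standard deviation.

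**How often the readings part.** At a 5% placebo rate the fallback is triggered in 2-20% of trials under A and 91-97% under B. At 10% the figures are 0.3-7% and 59-79%.

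**The case against.** The strongest reply is that this is a labelled sensitivity analysis and no decision rests on it. That is right: the chi-square p-value and the fixed-sequence testing in SAP 7.1.4 do not use it. A reader might infer that the primary result or its type I error is compromised; the documents do not support that. Coverage with no treatment effect is not part of this point.

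The estimator is also partly assumed. Adding 0.5 to each cell in the variance raises coverage to 90-94%. Pooled stratum variances give 93.2-94.7% at placebo rates of 10-15%, with little change at 1-5%. This stands, and it shows that the analysis is under-specified. Reading B is arguably strained, since one arm without responders does not stop the computation, so both ranges are given.

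Calling the interval simply too short would also be incomplete. At low placebo rates the lower limit is too high less often than its nominal 2.5%, and the main effect is to understate the drug.

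A reader might further infer that no CI method for the primary comparison was pre-specified, so that one could be picked after unblinding. The documents support only that the SAP names none. Protocol 10.8.1 places some statistical methods in the addendum, and SAP 1 places table specifications elsewhere. Little turns on it: for 15/62 against 4/62, Wald gives 5.5 to 30.0 points and Newcombe 5.1 to 30.3, and unstratified Wald covers about 94-95% at placebo rates of 2.5% or more.

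**Conclusion.** The point holds for the stratified sensitivity CI. With 62 per arm, unpooled observed variances, a common difference across strata and design-size effects, the nominal 95% interval covers about 86-92% under reading A and 87-93% under reading B. At placebo rates of 5% or more the ranges are about 89-92% and 92-93%. The lowest values need a placebo rate near 1%.

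Rates and stratum sizes are assumptions throughout, so the exact shortfall in this trial is not known. The cause does not depend on them: estimated variances in small strata set the weights. The missing CI method for the unstratified difference is a gap in detail and not an error.

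**What to change.** In SAP 7.3.1, and in the matching row of Table 7-2, replace the inverse-variance analysis with the Mantel-Haenszel risk difference and Sato 95% CI, stratified by both randomisation factors (four strata). Its weights depend only on the numbers of subjects, so it stays defined when a stratum has no responders. The two-strata fallback can then be deleted in both places, which also removes the ambiguity. SAP 7.3 repeats the word recognition analyses for W-22, so the change should carry over there.

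As a minor tidy-up, state in 7.3.1 and 7.8 that the unstratified difference in responder proportions (FX-322 minus placebo) is reported with a two-sided 95% Newcombe CI. Keep the unstratified chi-square as the primary test.

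The cost is SAP wording before unblinding and one changed sensitivity output, with a slightly wider interval. Data collection, sample size, the primary p-value and the testing order do not change.
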